#### **4.4.2. Analysis Methods**

##### **4.4.2.1. Renal Endpoints**

###### **4.4.2.1.1. Composite Endpoints**

The components of the renal composite endpoints, such as requirement for renal replacement therapy and doubling of serum creatinine, identified by the investigator or the sponsor for meeting the criteria pre-specified in the charter will be sent to the independent EAC.

The time to the first occurrence of each of the renal composite endpoints (see Section 4.4.1) will be analyzed in the ITT analysis set using a Cox proportional hazards model with treatment and baseline eGFR ( $< 60$ ,  $\geq 60$  mL/min/1.73m^2) as the explanatory variables. The hazard ratio of canagliflozin compared to placebo and its 95% confidence interval will be estimated from the model.

###### **4.4.2.1.2. Regression of Albuminuria**

Regression of albuminuria will be analyzed in a similar fashion in modeling and censoring rule as the analysis for progression of albuminuria. The analysis will be using the ITT analysis set based on ACR measurements from a single visit whether confirmed or unconfirmed. Subjects with normal albuminuria at baseline will be excluded. The hazard ratio of canagliflozin compared to placebo and its 95% confidence interval will be estimated from the model. Additionally, analyses based on confirmed regression plus unconfirmed regression from the last ACR values will be performed in a similar fashion using ITT analysis set.

###### **4.4.2.1.3. Urinary ACR**

Post-baseline ACR will be analyzed using mixed effect model repeat measurement (MMRM) and the ITT analysis set.

Since the distribution of ACR is highly skewed, the log transformed ACR values of all the post-baseline and scheduled visits will be modeled, using a linear mixed effects model. The linear mixed effects model will be fit to the logarithm of ACR as a dependent variable, including treatment, logarithm of baseline ACR value, visit, treatment by visit interaction, and logarithm of baseline ACR value by visit interaction as fixed effects. The percentage of treatment difference,

ie, treatment difference in mean ACR relative to placebo, can be calculated by taking the anti-logarithm of the estimated coefficient for the treatment group and subtracting 1. The ratio of mean ACR in treatment compared to placebo and its 95% CI will be presented. An unstructured covariance will be used to model the within subject errors.

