**Figure 2: Follow-up of Randomized Subjects with Respect to the GTED**

Note: Following the announcement of the GTED, investigators are not expected to continue collecting data for purposes of the clinical trial after the 30-day post-treatment contact.

In this study, duplicate urinary samples will be collected from 2 consecutive days (first morning void urine samples from the visit day and the day prior to the visit). The scheduled albumin creatinine ratio (ACR) measurements will be made on Day 1 (baseline), Week 26, Week 52, Week 78, Week 104, Week 156 and the last on-drug visit.

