### 2.3.3. Visit Windows

The Time and Events Schedule of the protocol indicates the visit timing and procedures (eg, laboratory, vital signs, and other key safety variables) for each visit; however, the timing of a subject's actual visit may not be exactly as per the protocol indicated target day / visit window. Consequently, for by-visit or over-time summaries, depending on the time period(s) involved in the summaries, the conventions outlined below will be used to allocate the data collected at each actual visit to a planned protocol visit by defining visit windows.

Baseline will be defined as the pre-dose measurement closest to or including Day 1 (prior to dose administration). If the pre-dose measurement on Day 1 is missing, the missing value will be imputed by the latest available measurement prior to Day 1. For serum creatinine, the average of the last 2 pre-dose measurement will be used as baseline.

If a subject has 2 or more actual visits in one analysis visit window, the visit closest to the target day will be used as the study visit for that analysis visit window. However, results from all visits will be included in the safety analyses (eg, pre-defined limits of change analysis) to assure that all results are included. If 2 study visits are the same number of days from the target day within the same visit window, the later visit will be considered the study visit for that target day. Even though all visits will be allocated an analysis visit window, only planned protocol visits for each variable will be included in the by-visit summaries or repeated measure analyses.

Note that the algorithms for calculating visit windows are the same for all the data periods (see Table 1). Table 2 summarizes the analysis visit windows for laboratory, vital signs, and other key safety variables.

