#### **Data for model development**

Due to the staggered enrollment of the study, for those randomized at a later stage of the enrollment period, pseudo visits up to the max possible visit week prior to GTED, i.e. week 130, will be created according to the protocol schedule. In addition, multiple data points at each visit, e.g. confirmatory samples, will be aggregated using geometric mean according to the variability of ACR data. There is small proportion of subjects (less than 2.5%) with unscheduled visits which will be combined with the closest scheduled visit using the same approach.

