#### **4.4.2.1.4. Change in eGFR**

For change in eGFR from baseline to the last off-drug measurement will be analyzed in the ITT analysis set using an analysis of covariance (ANCOVA) model with treatment and the baseline eGFR value as covariates. The treatment difference of canagliflozin compared to placebo in the least-squares means and associated 95% CI will be estimated from the model.

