#### **4.4.2.1.5. eGFR Slope**

The time slope of eGFR will be analyzed in the On-Treatment analysis set using a linear mixed effects model with eGFR as a dependent variable and treatment, baseline eGFR value, time (as a continuous variable), and treatment by time interaction as fixed effects and intercept and time as random effects. The parameter of interest is the coefficient for treatment by time interaction term, which measures the slope difference between canagliflozin and placebo over time.

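### The urinary ACR percentage difference is read from the treatment coefficient of a model with treatment-by-visit interaction, so its value depends on how visit is coded

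*SAP*

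**What the plan says.** SAP 4.4.2.1.3 (Urinary ACR) models post-baseline log ACR with an unstructured within-subject covariance. The model contains treatment, log baseline ACR, visit, "treatment by visit interaction, and logarithm of baseline ACR value by visit interaction as fixed effects". The percentage treatment difference is said to be obtainable from the anti-log "of the estimated coefficient for the treatment group and subtracting 1". The section then commits to a result: "The ratio of mean ACR in treatment compared to placebo and its 95% CI will be presented". It does not state the factor coding, a reference or target visit, averaging weights, or an adjusted-means contrast. Protocol 11.3.3 and the Synopsis give the same coefficient rule, also with treatment-by-visit interaction in the model.

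Two neighbouring sections do define their quantity. For change in eGFR (SAP 4.4.2.1.4) it is the difference "in the least-squares means and associated 95% CI will be estimated from the model". For eGFR slope (SAP 4.4.2.1.5): "The parameter of interest is the coefficient for treatment by time interaction term".

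The set of visits is also not settled. SAP 2.3.3 says that "only planned protocol visits for each variable will be included in the by-visit summaries or repeated measure analyses". SAP 1.1 schedules post-baseline ACR at "Week 26, Week 52, Week 78, Week 104, Week 156 and the last on-drug visit". The missing-data section (SAP 4.1.4.3, Data for model development) creates "pseudo visits up to the max possible visit week prior to GTED, i.e. week 130", and Week 130 is not a scheduled ACR visit.

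**The concern.** The coefficient rule is correct for a model without treatment-by-visit interaction. Once the interaction is added, the treatment main-effect coefficient changes meaning with the parameterisation, although the fit does not. Two programmers could follow the SAP exactly, obtain identical likelihoods, and report different percentage differences and confidence intervals because their software uses a different reference level.

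A single-visit effect could then be presented as the overall treatment difference. If the software takes the last level as reference, that effect may rest on a visit that few subjects reached. Because the contrast is unspecified, it could also be chosen after the data are seen. Urinary ACR is a listed objective and the continuous form of the measure behind the primary endpoint, so its main summary should not turn on a default setting.

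**Working it through.** The plan gives no numerical figure for this analysis, so there is nothing to reproduce. The argument is algebraic; the numbers show its size.

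**1. What the coefficient means.** Let treatment be 0/1 and let v index visits. The terms involving treatment are β_T·trt + γ_v·trt, so the treatment effect at visit v is β_T + γ_v.

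- Reference coding sets γ_ref = 0, so β_T is the effect at the reference visit only.
- Sum-to-zero visit coding sets Σγ_v = 0, so β_T is the equal-weight mean of the visit effects.

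The baseline-by-visit term does not involve treatment and does not change this.

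**2. Point estimate under an assumed drift.** Take ratios of 0.80, 0.82, 0.84, 0.86 and 0.90 at Weeks 26, 52, 78, 104 and 156 (assumed).

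- Week 26 reference: 0.80 − 1 = −20.0%.
- Week 156 reference: 0.90 − 1 = −10.0%.
- Sum-to-zero: the mean of the five logs is −0.1704, and exp(−0.1704) − 1 = −15.7%.

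**3. Fitted check.** One data set of 5,700 subjects was simulated. Subject and residual SDs on the log scale were both 0.6, follow-up was uniform over 78–160 weeks, and 273 subjects had Week 156 data. Assumed true differences were −22.1%, −18.1%, −13.9%, −11.3% and −4.9% over the five visits. The SAP's fixed effects were fitted with a random intercept in place of the unstructured covariance, which does not affect the coding argument. A second data set had a constant true effect of −16.5% (291 subjects at Week 156).

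| Visit coding | Varying effect: exp(coefficient) − 1 (95% CI) | Constant effect: exp(coefficient) − 1 (95% CI) |
|---|---|---|
| Week 26 reference | −22.6% (−26.0 to −19.2) | −16.8% (−20.4 to −13.1) |
| Week 156 reference | −15.2% (−27.6 to −0.6) | −19.4% (−30.9 to −5.9) |
| Sum-to-zero | −16.4% (−20.2 to −12.5) | −16.9% (−20.6 to −13.0) |

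The log-likelihood was −23539.147 for all three codings of the first data set and −23808.034 for all three of the second. These are the same fits read three ways.

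**4. Precision.** Assumptions: 2,850 per arm (5,700/2, protocol 11.2), SD of log ACR 0.75, within-subject correlation ρ of 0.5 to 0.7, follow-up uniform over 18–36 months, and 10% a year discontinuing. Standard errors come from the generalised-least-squares information for the visit means, with missing-data patterns simulated. The share of subjects observed at Weeks 26/52/78/104/156 is 94.9/90.0/85.5/54.2/0.5% with scheduled samples only. It is 96.2/93.6/87.7/69.3/12.7% if last on-drug samples are assigned by the SAP Table 2 windows.

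- *Week 26 reference* against the Week 26–104 average: 0.0203/0.0163 = 1.2 times (ρ = 0.5, windowed), and 1.1 times (ρ = 0.7).
- *Week 104 as last level* (Week 156 absent) against the same average: scheduled, 0.0248/0.0167 = 1.5 (ρ = 0.5) and 0.0232/0.0183 = 1.3 (ρ = 0.7); windowed, 1.4 and 1.2.
- *Week 156 reference, windowed*, against the Week 26–104 average: 0.0451/0.0163 = 2.8 (ρ = 0.5) and 0.0375/0.0180 = 2.1 (ρ = 0.7). Against the five-visit average: 0.0451/0.0179 = 2.5 and 0.0375/0.0189 = 2.0.
- *Week 156 reference, scheduled only*, against the five-visit average: 0.2245/0.0476 = 4.7 (ρ = 0.5) and 0.1762/0.0394 = 4.5 (ρ = 0.7).

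**The case against.** The SAP describes its target as a difference or ratio in mean ACR and says only that it can be obtained from the coefficient. A statistician would probably compute adjusted means. Nor does the text say that only one overall ratio will be shown; visit-specific ratios would be compatible with an endpoint described as change over time. The other repeated-measures analysis, HbA1c in SAP 4.4.2.2, also names no visit or weights, so ACR is not unusual in that respect. The SDs, correlations and drift are not in the documents, and the largest ratios need an analyst to accept a reference visit with almost no data. The Week 130 statement belongs to the imputation for the primary endpoint, not to this model. If Week 130 were the last level through windowing (about 27% of subjects), the standard-error ratio would be about 1.5 to 2.0, smaller than for Week 156.

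Much of this stands as a limit on weight. The ordinary cases are the 1.1 to 1.5 range, and the spread in point estimates comes from the assumed drift. It does not remove the problem. The coefficient is the only route the plan gives, and a reading as adjusted means still leaves the visit or weights open. The HbA1c section is silent on the contrast but does not prescribe a coefficient that may be the wrong quantity.

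**Conclusion.** The concern holds. Followed literally under reference coding, the rule reports the effect at one arbitrary visit as the treatment difference, and no other section of the protocol or SAP resolves which visit or average is meant. This follows from the model as written and needs no assumption. The size does need assumptions: nothing in expectation if the effect is constant over visits, −20% against −10% under the illustrated drift, and an interval from slightly to more than twice as wide as that for a Week 26–104 average, depending on the reference visit. The scheduled-only Week 156 figure of about 4.5 to 4.7 times is an extreme case.

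The consequence is small. Urinary ACR is exploratory and its tests are nominal (SAP 4). The primary Cox analysis, the gatekeeping sequence and the sample size are unaffected. It should be corrected because the correction is almost free.

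**What to change.** Replace the coefficient rule in SAP 4.4.2.1.3 with a named least-squares-means contrast in log ACR. One suitable choice is the equal-weight average of the treatment differences over Weeks 26, 52, 78 and 104, with the visit-specific differences alongside; a difference at one named visit would also serve. Exponentiate the contrast and its 95% confidence limits to give the ratio of adjusted geometric means, and subtract 1 for the percentage difference. State whether Week 156 enters the model when few or no values exist there, and how last on-drug samples are assigned to visits. Make the same change in protocol 11.3.3 and the Synopsis. It would be sensible to name the HbA1c contrast in SAP 4.4.2.2 at the same time.

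The cost is one sentence in each place and one contrast statement in the program. Data collection and the confirmatory analyses do not change. The contrast should be fixed before unblinding.

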#### **4.4.2.1.4. Change in eGFR**

For change in eGFR from baseline to the last off-drug measurement will be analyzed in the ITT analysis set using an analysis of covariance (ANCOVA) model with treatment and the baseline eGFR value as covariates. The treatment difference of canagliflozin compared to placebo in the least-squares means and associated 95% CI will be estimated from the model.

#### **4.4.2.1.5. eGFR Slope**

The time slope of eGFR will be analyzed in the On-Treatment analysis set using a linear mixed effects model with eGFR as a dependent variable and treatment, baseline eGFR value, time (as a continuous variable), and treatment by time interaction as fixed effects and intercept and time as random effects. The parameter of interest is the coefficient for treatment by time interaction term, which measures the slope difference between canagliflozin and placebo over time.

#### **4.4.2.2. Changes in HbA1c**

Change in HbA1c from baseline will be analyzed using MMRM and the ITT analysis set. The effect of canagliflozin relative to placebo on the changes in HbA1c from baseline over time will be assessed using MMRM. The analysis will include the fixed categorical effects of treatment, visit, and treatment-by-visit interaction, as well as the continuous, fixed covariates of baseline and baseline-by-visit interaction. An unstructured covariance will be used to model the within subject errors.

#### **4.4.2.3. AHA Utilization**

Summary of AHA utilization is described under Section 3.5.

### **5. SAFETY**

The safety analysis will be mainly based on the On-Treatment analysis set unless otherwise specified.

There will be no imputation of missing values for clinical laboratory test results, vital sign measurements in the safety analyses.

#### **5.1. Adjudicated MACE Events**

The MACE is the composite of CV outcomes including CV death, non-fatal MIa, or non-fatal stroke. Adjudication of these outcomes by the EAC has been done in a blinded fashion.

---

a Silent MIs are excluded from the analysis.

### **5.1.1. Analysis Methods**

The analysis will be based on the time to first occurrence of MACE using the ITT analysis set. The HR of all canagliflozin compared to placebo and its 95% CI will be estimated using a stratified Cox proportional hazards regression model with treatment (all canagliflozin and placebo) as the explanatory variable, and prior CV disease subgroup (secondary prevention and primary prevention) as the stratification factors. P-value of stratified log rank test for treatment effect will also be reported for the primary analysis.

### **5.1.2. Supplementary Analysis**

A prior post-hoc analysis performed by the FDA of the MACE-plus events occurring during the first 30 days post-randomization in CANVAS showed an imbalance in favor of placebo. In the PMR, FDA requested that the pattern of MACE events occurring in the first 30 days post randomization in CANVAS-R be explored. Additional examination of the MACE events in the first 60 and 90 days using the ITT analysis set will be made.

An excess of volume depletion AEs in the canagliflozin groups could provide a possible biologic basis for an imbalance in MACE events between canagliflozin and control. In the CANVAS study, the Kaplan-Meier (KM) time-to-event analysis comparing canagliflozin and placebo showed that the greatest separation in the curves for volume depletion AEs occurred during the first 90 days post-randomization.

To assess the potential association between MACE events and volume depletion AEs and fulfill the PMR request, hazard ratio will be estimated using the same stratified Cox model as in the main analysis (see Section 5.1.1) for events occurring within the first 30 days, and within the first 90 days post-randomization. In addition, Kaplan-Meier plots including data within first 30 days and first 90 days will be presented.

Additionally, time to the first occurrence of each component of MACE as well as fatal/non-fatal MI and fatal/non-fatal stroke will be analyzed using the same Cox model described in Section 5.1.1.

## **5.2. Adverse Events**

Adverse events (AEs) will be coded using the latest version of the Medical Dictionary for Regulatory Activities (MedDRA) at the time of database lock.

A treatment-emergent AE (TEAE) is defined as an AE with an onset after the initiation of double-blind study drug and before the last study medication date plus 30 days. AEs with a start date prior to initiation of double-blind study drug which are subsequently reported to have either an increase in intensity or change in attribution in relationship to study drug (ie, attribution to possible, probably, very likely) after the initiation of double-blind study drug will also be considered as TEAEs.

### 5.2.1. Adverse Event Collection

The AE collection in CANVAS-R is streamlined to include serious adverse events (SAEs), AEs that lead to study drug discontinuation, and all AEs (serious and non-serious) for selected AEs of interest ([Table 3](#), Section B).

For selected AEs of interest, additional data will be collected on supplementary CRF pages mainly for the purposes of narrative description of certain events. [Table 3](#) lists the AEs of interest.

**Table 3: Adverse Events of Interest**

**Section A: For the AEs listed below, only serious AEs or AEs that led to drug discontinuation were collected:**

- Osmotic diuresis
- Volume depletion
- Hypoglycemia
- Urinary tract infection (UTI)
- Female mycotic genital infection
- Severe hypersensitivity /cutaneous reactions
- Pancreatitis
- Hepatic injury
- Renal related AEs (including Nephrotoxicity/ acute kidney injury)

**Section B: The AEs listed below were collected regardless of whether they were serious and/or led to study drug discontinuation for the study:**

- Male mycotic genital infection (balanitis, phimosis, events leading to circumcision)
- Malignancy
  - Renal cell cancer
  - Bladder cancer
  - Pheochromocytoma
  - Leydig cell tumors
  - Breast cancer
- Photosensitivity
- Venous thromboembolic events (VTE)
- Amputation
- Fracture
- Diabetic Ketoacidosis

The AEs listed above will be identified using a MedDRA preferred term list ([Appendix 1.3](#)).

### 5.2.2. Analysis Methods

The study duration of CANVAS-R is long relative to the rest of the canagliflozin Phase 3 program. Accordingly, the incidences of AEs (ie, proportion of subjects reporting the AEs) derived from the study are not comparable to the incidences generated in the Phase 3 program. Therefore, the exposure-adjusted incidence rate will be reported in addition to the incidence. The rate is calculated as the total number of subjects with the AE divided by the On-treatment exposure in subject-years. For some particular AEs such as malignancy where the off-drug follow

up is included, the follow-up-adjusted incidence rate will be estimated. The rate is calculated as the total number of subjects with the AEs divided by the total follow-up time in subject-years.

For general AEs and selected AEs of interest that are not routinely collected in CANVAS-R (refer to Section A of [Table 3](#)), the main interest will be the serious AEs and the AEs leading to discontinuation of study medication.

#### **5.2.2.1. General Adverse Events**

An overview summary table with the incidence and the exposure-adjusted incidence will be provided for:

- Serious AEs;
- Deaths;
- AEs leading to discontinuation of study medication;
- Serious AEs leading to discontinuation of study medication;
- Serious AEs considered drug-related;
- AEs considered drug-related leading to discontinuation of study medication.

SAEs by system organ class and preferred term will be summarized by treatment group using the On-Treatment analysis set. The same summary will be provided for AE leading to discontinuation of study medication using the On-Treatment analysis set.

The incidence of all SAEs (by preferred term, grouped by SOC, and presented by treatment group) will also be summarized by the relationship to study drug, by the action taken regarding the study drug, as well as by the outcome. The relationship to study drug will be presented by 2 categories: related (which includes possibly related, probably related and very likely related, as reported by the investigator) and not related (which includes not related and doubtfully related, as reported by the investigator).

For reference, as a screening tool, the 95% CIs for incidence difference between treatment groups will be calculated for the AEs which are reported in at least 4 or more subjects in any treatment group. Four (rule-of-4) was chosen based on the recommendation from the Safety, Planning, Evaluation, and Reporting Team (SPERT). The exclusion of “0” from the 95% CI for the between-group difference in incidence for a particular AE does not necessarily imply that the difference is due to drug. The intent of providing the 95% CIs is as a filter to identify AEs that require additional assessment. AEs identified by the above screening procedure will be presented and may be subject to further evaluation.

Listings will also be provided for deaths, SAEs, and AEs leading to study drug discontinuation.

For AEs of interest in Section A of [Table 3](#), a summary similar to the analysis of general AEs will be provided. The AEs will be identified using the MedDRA preferred terms listed in [Appendix 1.3](#).

